#### 17.2.3. **Analysis of Secondary Efficacy Variables**

#### 17.2.3.1. PROPORTION OF PASI 50, PASI 75, PASI 90 AND PASI 100 RESPONDERS AT WEEK 28

Number and proportion of patients with a PASI 50, PASI 75 and PASI 90 response at Week 28 will be presented by treatment groups. The difference in proportions will be calculated as the difference between the observed proportions in each treatment group. An asymptotic 2-sided 90% confidence interval for the difference of proportions will be obtained using the Wald method. Additionally, a descriptive statistics table of PASI total score will be provided by treatment group for observed value, change from baseline and percent improvement from baseline for each postbaseline visit. Also, the number and proportion of patients with a PASI 50, PASI 75 and PASI 90 response based on observed value at each post-baseline visits will be presented by treatment groups.

\\ieedc-vnasc01\Biosdata\Viatris\HULIO\HAB34991\Biostatistics\Documentation\SAP Document:

2.0 Author: Version Number:

> Version Date: 29Nov2023

Template No.: CS\_TP\_BS016 Revision 7 Reference: CS\_WI\_BS005

Page 33 of 48

#### 17.2.3.2. PROPORTION OF SPGA SUCCESS (CLEAR OR ALMOST CLEAR) AT WEEK 28

Number and proportion of sPGA success will be analyzed same as PASI response.

The number and proportion of patients with a sPGA scores (Clear, almost clear, Mild, Moderate, Moderate to severe, Severe) and sPGA success response based on observed value at each post-baseline visits will be presented by treatment groups.

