### 2.2.2. Secondary Endpoints

The secondary endpoints are:

- Other adalimumab PK parameters, including Tmax, 26-28 and Cmin, 26-28 during the intensive PK sampling interval between Weeks 26 and 28 and Ctrough obtained at the scheduled PK sample time points.
- Proportion of PASI 50, PASI 75, PASI 90 and PASI 100 responders at Week 28
- Proportion of sPGA success (clear or almost clear) at Week 28
- Safety measures characterized by type, incidence, severity, timing, seriousness and relatedness of treatmentemergent adverse events (TEAEs) including injection site reactions [ISRs], hypersensitivity reactions, heart failure, malignancies, serious infections including tuberculosis [TB], and laboratory test abnormalities
- Incidence of positive anti-drug antibody (ADA) and neutralizing antibody (NAb) response and ADA titers at Week 28

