#### 7.5. Statistical Tests

Confidence intervals will be 90% and all tests will be two-sided, unless otherwise specified in the description of the analyses.

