#### 17.2.2. Data Imputation for Secondary Efficacy Variable(s)

Missing data will be handled using a combination of non-responder imputation and multiple imputation methods. After applying multiple imputation, non-responder imputation will be performed.

Multiple imputation (MI) is a simulation-based approach where missing values are replaced by multiple Bayesian draws from the conditional distribution of missing data given the observed data and covariates, creating multiple completed data sets. These completed data sets can then be analyzed using standard methods. Rubin (1987) presented rules how to combine the multiple sets of estimates to produce overall estimates and confidence intervals that

Document: \\ieedc-vnasc01\Biosdata\Viatris\HULIO\HAB34991\Biostatistics\Documentation\SAP

Author: Version Number: 2.0

Version Date: 29Nov2023

Template No.: CS\_TP\_BS016 Revision 7 Reference: CS\_WI\_BS005

Template No.: 00\_11 \_D0010 Nevision /

Page 30 of 48

adequately incorporate missing data uncertainty. Below steps will be applied on the PASI score and the sPGA separately.

Step 1: Creation of multiple imputed data sets

The first step of the multiple imputation is to transform a non-monotone missing data structure to a monotone one. Intermediate missing variables will be multiple imputed using the Markov Chain Monte Carlo (MCMC) method and assuming Missing at Random (MAR) and multivariate Normality. The SAS procedure PROC MI with the MCMC option will be used. Missing values for the 'change from baseline PASI score' or 'sPGA score' will be imputed. The change from baseline in PASI score appears to follow closer to a normal distribution than the actual PASI score. Assuming normality for the 'sPGA score' as well. This step will be performed on longitudinal continuous change from baseline PASI score or sPGA score between Baseline and week 28 (Week 12, 16 and 20 inclusive).

For each variable, the imputations will be done separately for each randomized treatment group including baseline weight as additional covariate.

The number of imputations will be set to 500. The SAS code used to generate the multiple imputed data sets will be like that shown below:

The input data set <Efficacy> should have one record per patient with baseline PASI score or sPGA score as well as all changes from baseline PASI or post baseline sPGA score.

(A) - Creation of monotone missing data structure

PROC MI DATA=<Efficacy> OUT=<impdata> SEED=3001 NIMPUTE=500;

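### Every between-arm Week 28 efficacy interval rests on a responder cut, while continuous PASI, already imputed 500 times, gets no arm difference: a loss of precision in a supportive estimate

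*SAP*

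**What the plan says.** Efficacy in the switching arm against the non-switching arm belongs to the secondary objective. SAP 2.2.2 defines the PASI endpoint as "Proportion of PASI 50, PASI 75, PASI 90 and PASI 100 responders at Week 28" and adds sPGA success (clear or almost clear). Each of these is a cut of a score.

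For the comparison, SAP 17.2.3.1 states: "The difference in proportions will be calculated as the difference between the observed proportions in each treatment group". It continues: "An asymptotic 2-sided 90% confidence interval for the difference of proportions will be obtained using the Wald method". The Efficacy Analysis paragraph of the protocol synopsis says the same. The heading of 17.2.3.1 includes PASI 100, whereas its body lists PASI 50, 75 and 90. Section 17.2.3.2 treats sPGA success in the same way.

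The continuous score is used in two places.
- In 17.2.2 Step 1: "Missing values for the 'change from baseline PASI score' or 'sPGA score' will be imputed", and "This step will be performed on longitudinal continuous change from baseline PASI score or sPGA score between Baseline and week 28". There are 500 imputations. The code that follows turns each completed value into responder status, and only that status reaches PROC MIANALYZE in Steps 4 to 6.
- In 17.2.3.1: "a descriptive statistics table of PASI total score will be provided by treatment group for observed value, change from baseline and percent improvement from baseline". This table is descriptive, uses observed values and contains no arm difference.

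SAP 17.3 plans no exploratory efficacy analysis.

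**The concern.** A cut treats a patient at 76% improvement and one at 99% as the same PASI 75 responder. Only patients with at least a PASI 50 response at Week 12 are randomised, so high Week 28 response rates are plausible, and lower cuts then become insensitive. If switching raised residual disease while leaving most patients above 75% improvement, a responder difference would show it less clearly than the mean percent improvement.

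The Week 12 score is a pre-randomisation value. The primary PK model in SAP 20.2.7 already adjusts for the log ratio of Week 12 to Week 1 PASI, but the efficacy comparison uses no such adjustment. What is at stake is how precisely the trial can describe efficacy after switching.

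**Working it through.** **The plan's own figure.** The only sample-size figure concerns PK (SAP 4). Inputs: mean ratio 0.935, CV 0.38, limits 0.80 to 1.25, 5% per one-sided test, target power 0.9487 per endpoint. It reproduces: N = 282, power 0.9496 per endpoint, joint power 0.9496² = 0.902. Then 280/(1 − 0.15) = 329.4, so 330 randomised, and 330/(1 − 0.10) = 366.7, so about 370 enrolled. The 280 evaluable patients give 140 per arm, used below. The documents give no size for the per-protocol efficacy population and no response rate, effect size, margin or power for efficacy.

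**Criterion.** How often the 90% interval for the arm difference excludes zero. The level comes from SAP 7.5 ("Confidence intervals will be 90% and all tests will be two-sided"). The plan does not make this test; it serves here as a measure of precision.

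**Check 1: normally distributed score, mean shift of d SD (assumed).**
- Continuous power = Φ(d√(n/2) − 1.645). At d = 0.3: 0.3 × √70 = 2.510, and Φ(0.865) = 81%.
- PASI 75 with a reference rate of 80%: the switching rate is Φ(0.842 − 0.3) = 0.706, SE = √[(0.80 × 0.20 + 0.706 × 0.294)/140] = 0.0512, and Φ(0.094/0.0512 − 1.645) = 58%.
- The loss is 81 − 58 = 23 points. Over d = 0.2 to 0.4 and rates of 60% to 85% it runs from 10 to 27 points.

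**Check 2: lognormal Week 28/baseline PASI ratio (assumed).** Median 0.05 to 0.12, log-SD 0.9 to 1.2, switching-arm ratio multiplied by 1.3, correlation with Week 12 of 0.3 or 0.6. Example with median 0.10 and log-SD 0.9:
- PASI 75: Φ(ln(0.25/0.10)/0.9) = 0.846 against Φ(ln(0.25/0.13)/0.9) = 0.766. SE = 0.0470, and power is about 52%.
- PASI 90: 0.500 against Φ(ln(0.10/0.13)/0.9) = 0.385. SE = 0.0590, and power is about 62%.
- Simulation at correlation 0.6: PASI 75 50.7%, PASI 90 59.8%, unadjusted mean percent improvement 65.4%, ANCOVA on Week 12 percent improvement 77.2%. With no true difference, all four reject at 9 to 11%.

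The gain splits into two parts. Against PASI 75, avoiding the cut gives 65.4 − 50.7 = 14.7 points, and Week 12 adjustment gives a further 77.2 − 65.4 = 11.8. Against PASI 90, avoiding the cut gives 65.4 − 59.8 = 5.6 points, with the same 11.8 from adjustment.

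**Across settings, 30% higher residual PASI:**

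| ANCOVA gain over | No added clear patients | 25% clear in both arms |
|---|---|---|
| PASI 75 | about 14–16 points (correlation 0.3), 19–28 (0.6) | about 6–16 points |
| PASI 90 | about 1–19 points | about 1–13 points |

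The lower ends are soft. A repeat simulation with 25% clear put the gain over PASI 90 at −2 to +2 points at correlation 0.3.

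**Smaller effect.** With residual PASI 20% higher, detection is 19–35% for PASI 75, 25–40% for PASI 90 and 26–52% for ANCOVA. No method is reliable there.

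**Without Week 12 adjustment.** With a skewed ratio (log-SD 1.0), a t test on percent improvement gains 5 to 17 points over PASI 75 at rates of 70% to 90%, and 1 to 10 points when 20% to 35% of patients are clear.

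**The case against.** The strongest reply is that no planned power is lost. Efficacy has no hypothesis, margin or assumed rate, and the sample size and success rule rest on AUC and Cmax alone. That stands. A reader might infer that the plan forfeits a fixed 10 to 27 points of power. The documents do not support this: every efficacy input is assumed, and the range moves with effect size, response rate, skewness and the share of clear patients.

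Second, PASI 75 is a favourable comparator for this argument. PASI 90 is also planned with an interval. The unadjusted mean beats it by only about 0 to 8 points, and when both are adjusted for Week 12 the gap is about 1 to 9. So a reader should not infer that all the planned intervals are of low precision.

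Third, the by-arm table supplies n, mean and SD (SAP 8), from which an unadjusted observed-case difference can be computed by hand. That is true, but such a difference is not pre-specified, imputed or adjusted.

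Fourth, the endpoints are the protocol's own. That is a reason to keep them, and it does not bar a supportive addition. Only the synopsis of the protocol was available, so nothing is claimed here about whether its body or any guideline calls for responder cuts.

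Finally, the imputed data sets are not ready for this use. The text of 17.2.2 says imputation is done separately by arm, but the Step 1(B) code lists treatment in CLASS and not in VAR or BY, which pulls imputed values towards no arm difference. The normal imputation is also unbounded: draws beyond −100% leave a responder cut unchanged but distort a mean. These points stand and shape the fix.

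**Conclusion.** The point holds as a low-cost improvement to a supportive analysis. The plan imputes a continuous outcome, discards its scale before any between-arm comparison, and leaves the Week 12 score out of that comparison.

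Under the stated assumptions (140 per arm, lognormal ratio, 30% higher residual PASI), the adjusted continuous analysis detects a difference about 14 to 28 points more often than PASI 75, or about 6 to 16 if 25% of patients are clear. Against PASI 90 the figures are about 1 to 19 and 1 to 13, and the gain can vanish when clearance is high and the Week 12 correlation low. Part of every figure is due to covariate adjustment, and the gain is smaller for a 20% difference.

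A reader might go further and infer that the trial is underpowered for efficacy or that its interchangeability conclusion is weakened. Neither follows: no efficacy power is claimed, and the conclusion rests on PK.

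**What to change.** Keep all responder endpoints, and make three changes to the SAP.

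1. In 17.2.2 Step 1(B), impute by treatment group as the text already states (add treatment to BY or VAR), and limit imputed PASI to its valid range.
2. In 17.2.3.1, add a supportive analysis: in each completed data set, an ANCOVA of percent change from baseline in PASI at Week 28 with treatment, baseline PASI and Week 12 percent change. Combine the results with PROC MIANALYZE (ALPHA=.10) and report the adjusted arm difference with its 90% CI.
3. State that this analysis assumes data missing at random for patients who discontinue, and report the non-responder analysis (Step 2) alongside it. Do not label it the main efficacy comparison.

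The cost is SAP wording, a correction to the imputation code, and one modelling and one combining step. No new data, visits or patients are needed. The downsides are reliance on the missing-at-random assumption for discontinuers, and on large-sample normality for a percent change that is skewed towards full clearance.

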Sensitivity Analyses: The AUC τ , $_{26\text{-}28}$ and C_{max} , $_{26\text{-}28}$ will be analysed using analysis of covariance (ANCOVA) model on the log transformed scale. This model will include treatment and covariates. Log transformed AUC $_{\tau,\ 10\text{-}12}$ or $C_{max,\ 10\text{-}12}$ will be used as covariates.

The secondary PK endpoint $C_{min\ 26-28}$ will be analyzed in the same way as the primary endpoints. However, even the mean ratio and CIs will be calculated and presented. No formal conclusion is required to be within BE limits.

The secondary PK endpoint $T_{max\ 26-28}$ will be analyzed in a descriptive manner only.

All PK analysis will be performed on the PK population.

Efficacy Analysis:

All secondary efficacy endpoint analyses will be based on the PP population.

The difference in proportions will be calculated as the difference between the observed proportions in each treatment group. An asymptotic 2-sided 90% confidence interval for the difference of proportions will be obtained using the Wald method.

Safety Analyses:

Treatment-emergent AEs, serious AEs and Adverse event of special interest (AESI) will be descriptively summarized by system organ class, preferred term, and treatment group.

Overall, descriptive summaries will be produced as well as according to severity and relationship to the study treatment.

Local tolerance and antibodies to adalimumab will be descriptively summarized by treatment group.

The safety analyses will be performed on the Safety and Run-in Period populations.

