#### Screening Period:

Patients will be enrolled into the study after successfully completing screening activities between Day -21 to Day -1. Run-in Period:

Patients will receive Humira (initial dose of 80 mg [ $2 \times 40$  mg]; Day 1, Week 1) administered subcutaneously (SC), followed by 40 mg SC given every other week starting 1 week after the initial dose (last dose at Week 10/Visit 6).

Document: \\ieedc-vnasc01\Biosdata\Viatris\HULIO\HAB34991\Biostatistics\Documentation\SAP

Author: Version Number: 2.0

Version Date: 29Nov2023

Template No.: CS\_TP\_BS016 Revision 7 Reference: CS\_WI\_BS005

Page 13 of 48

Randomized Interchangeable Treatment Period:

Patients achieving at least a PASI 50 response at beginning of Week 12 /Visit 7 will be randomly assigned in a 1:1 ratio to either of the following groups for participation in the Randomized Interchangeable Treatment Period:

Group 1: Patients continue to receive Humira (40 mg every other week) until Week 26 /Visit 14.

Group 2: Patients undergo repeated switches until Week 26 /Visit 14:

- Hulio (40 mg every other week) for 4 weeks,
- Humira (40 mg every other week) for 4 weeks, and
- Hulio (40 mg every other week) for 8 weeks.

Randomization will be stratified based on Week 12/ Visit 7 PASI response:  $\geq$  PASI 50 to  $\leq$  PASI 75 or  $\geq$  PASI 75. Last dose in the Randomized Interchangeable Treatment Period will be at Week 26. Follow-up safety assessment will be done 4 weeks post last dose of study drug treatment received during the Randomized Interchangeable Treatment Period. The last efficacy and PK assessments are at start of Week 28/ Visit 15.

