#### 17.2.1. Secondary Efficacy Variables & Derivations

17.2.1.1. PROPORTION OF PASI 50, PASI 75, PASI 90 AND PASI 100 RESPONDERS AT WEEK 28 A PASI 50, PASI 75, PASI 90, and PASI 100 response is defined as a  $\geq$  50%,  $\geq$  75%,  $\geq$  90% and  $\geq$  100% improvement of PASI score from baseline (Week1/ Visit1).

Document: \\ieedc-vnasc01\Biosdata\\Viatris\HULIO\HAB34991\Biostatistics\Documentation\SAP

Author: Version Number: 2.0

Version Date: 29Nov2023

Template No.: CS\_TP\_BS016 Revision 7 Reference: CS\_WI\_BS005

Effective Date: 01Nov2021

Page 29 of 48

=	PASI50	)		a	t			Week				X:
	Yes	if	percent	change	of	PASI	score	at	Week	X	≤	-50
	No if p	ercent (	change of PA	SI score at W	eek X >	-50						
-	PASI75	5		a	t			Week				X:
	Yes	if	percent	change	of	PASI	score	at	Week	X	<	-75
	No if p	ercent (	change of PA	SI score at W	eek X >	-7 5						
-	PASI90	)		a	t			Week				X:
	Yes	if	percent	change	of	PASI	score	at	Week	X	<	-90
	No if p	ercent (	change of PA	SI score at W	eek X >	· - 90						
(17)	PASI10	00		:	at			Week				X:
	Yes	if	percent	change	of	PASI	score	at	Week	X	≤	-100
	No if p	ercent	change of PA	SI score at W	eek X >	-100						

where, percent change of PASI score (%) at Week X = [(PASI score at Week X - PASI score at Baseline)/ PASI score at baseline] x100)).

Example, if percent change of PASI score (%)  $\leq$  - 90 then it would be considered as PASI 90 responder.

### 17.2.1.2. PROPORTION OF SPGA SUCCESS (CLEAR OR ALMOST CLEAR) AT WEEK 28

The sPGA is used to determine the patient's psoriasis lesions overall at a given time point. It will be used to assess the improvement in the overall severity of the disease in individual patients and thus arrive at the number and percentage of patients achieving sPGA responses of clear (0) or almost clear (1).

- sPGA Success at Week X
- Yes, if sPGA response at Week  $X \le 1$
- No, if sPGA response at Week X > 1

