#### Step 3: Calculation of proportion in each treatment arm for each imputed data set

PROC FREQ DATA=<Inpdata>;

TABLES <PASI X Category> /binomial(LEVEL=1 CL=WALD) alpha=0.10;

BY Imputation <treatment group>;

ODS OUTPUT BINOMIAL=prop;

RUN:

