### Step 4: Combining proportion estimates in each treatment arm and the difference between proportions

For the proportions, the proportion estimates and their asymptotic standard errors provided by PROC FREQ for each imputed data set can be passed directly to PROC MIANALYZE.

PROC MIANALYZE DATA=<PROP> ALPHA=.10;

MODELEFFECTS < Proportion>;

STDERR <Standard error>;

Document: \\ieedc-vnasc01\Biosdata\Viatris\HULIO\HAB34991\Biostatistics\Documentation\SAP

Author: Version Number: 2.0

Version Date: 29Nov2023

Template No.: CS\_TP\_BS016 Revision 7 Reference: CS\_WI\_BS005

Effective Date: 01Nov2021

Page 32 of 48

BY <treatment group>; ODS OUTPUT PARAMETERESTIMATES=<OUTPUTDATA>; RUN:

For the difference between proportions in two arms, the standard error of the estimated difference is computed as the square root of the sum of squared standard errors for each proportion. This standard error is then passed to PROC MIANALYZED along with the estimated difference in proportions.

Step 5: Compute estimates of the difference in proportions of responders between treatment arms and their standard errors

```
DATA prop diff;
MERGE < Treatment group 1 data > < Treatment group 2 data >
BY Imputation;
prop diff = (p1-p2);
se_diff = sqrt(se1*se1 + se2*se2);
RUN;
```

Step 6: Combine estimates of the proportion differences

```
PROC MIANALYZE DATA=prop_diff> ALPHA=.10;
MODELEFFECTS  diff>;
STDERR <se diff>;
ODS OUTPUT PARAMETERESTIMATES=mian_prop_diff;
RUN;
```

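### PASI 50 at Week 28 has a ceiling built in by the randomisation rule, yet Wald is the only interval planned; the loss is small for the difference and larger for the per-arm limits.

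*SAP*

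**What the plan says.** - **Entry to randomisation (SAP 3.1).** "Patients achieving at least a PASI 50 response at beginning of Week 12 /Visit 7 will be randomly assigned in a 1:1 ratio".
- **Endpoint (SAP 17.2.1).** PASI 50, 75, 90 and 100 at Week 28 are each defined by "improvement of PASI score from baseline (Week1/ Visit1"), the same reference point as the entry rule.
- **Interval for the difference.** The protocol synopsis (Efficacy Analysis) states: "An asymptotic 2-sided 90% confidence interval for the difference of proportions will be obtained using the Wald method". SAP 17.2.3.1 repeats that a "confidence interval for the difference of proportions will be obtained using the Wald method", and SAP 7.5 sets the level: "Confidence intervals will be 90% and all tests will be two-sided".
- **Per-arm code (SAP 17.2.2, Step 3).** "binomial(LEVEL=1 CL=WALD) alpha=0.10". Step 4 passes the per-arm proportions and asymptotic standard errors to PROC MIANALYZE by treatment group at alpha 0.10.
- **Pooled difference (SAP 17.2.2, Steps 5 and 6).** "se_diff = sqrt(se1*se1 + se2*se2"), combined over 500 imputations.
- **Non-responders (SAP 17.2.2, Step 2).** Patients who stop treatment or are lost before Week 28, or who have a severe therapy violation affecting efficacy assessment, count as failures.
- **Analysis set (SAP 17.2 and 6.5).** Per protocol. It requires at least one post-randomisation efficacy assessment, and non-compliance with treatment is a possible reason for exclusion.

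Neither document names another method for proportions close to 1.

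**The concern.** The entry rule admits only patients who already meet the PASI 50 threshold, and both arms stay on adalimumab. Week 28 PASI 50 therefore measures whether an existing response was kept, and a high proportion is the natural expectation. Near 1 the Wald standard error, sqrt(p(1-p)/n), is unreliable: it shrinks with the observed failures, the limits can pass 100%, and it is exactly zero when an arm has no failures.

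The intervals describe whether efficacy is preserved under switching. If they are too narrow they understate the uncertainty, and an arm with no failures would invite a change of method after the data are seen.

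**Working it through.** The plan gives no expected rate and no operating characteristics for these intervals, so there is no figure of its own to reproduce. The response rates below are assumptions shown over a range.

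**Inputs.** SAP section 4 randomises 165 per arm and expects 280 evaluable, so 280/2 = 140 per arm. That count was derived for PK, and the per-protocol set may differ. The level is 90%, z = 1.645.

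**Plausible rates.** If 5% discontinue and 2% of the rest lose response, the rate is 0.95 × 0.98 = 0.931. If 15% are non-responders for any reason, it is 85%. With few dropouts it could be 97% or more.

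**Formulas.**
- Wald, one arm: p ± z·sqrt(p(1-p)/n).
- Wald, difference: d ± z·sqrt(se1² + se2²).
- Newcombe: d - sqrt((p1-l1)² + (u2-p2)²) to d + sqrt((u1-p1)² + (p2-l2)²), where l and u are Wilson limits.

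Coverage is the exact sum of binomial probabilities over all outcomes whose interval contains the true value. One completed data set is modelled; between-imputation variance is not.

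**Difference, 140 per arm, nominal 0.90.**

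| True rates | Wald | Newcombe | P(Wald has zero width) |
|---|---|---|---|
| 85% v 85% | 0.897 | 0.901 | negligible |
| 90% v 90% | 0.896 | 0.904 | negligible |
| 95% v 95% | 0.889 | 0.913 | 6e-7 |
| 97% v 97% | 0.880 | 0.926 | 0.0002 |
| 98% v 98% | 0.874 | 0.938 | 0.003 |
| 98.5% v 98.5% | 0.881 | 0.951 | 0.015 |
| 99% v 99% | 0.909 | 0.972 | 0.060 |
| 99.5% v 99.5% | 0.966 | 0.994 | 0.25 |
| 99% v 97% | 0.876 | 0.912 | 0.003 |
| 99.5% v 97.5% | 0.845 | 0.920 | 0.014 |

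Zero width needs no failures in either arm, so its probability is (p1·p2)^140. With 165 per arm the equal-rate Wald results are similar (0.889 at 95%, 0.874 at 98%). The lowest value in the wider grid is 0.829, at 99.8% v 98% with 165 per arm.

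**Per arm, coverage averaged over n = 130-165.**

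| True rate | Wald |
|---|---|
| 95% | 0.877 |
| 97% | 0.854 |
| 98% | 0.791 |
| 99% | 0.765 (minimum 0.719) |
| 99.5% | 0.518 |

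Wilson averages 0.89-0.95 over the same rates. Per-arm Wald coverage does not fall smoothly as the rate rises: at n = 140 it is 0.765 at 98% but 0.874 at 98.5%.

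**Limits above 100%.** With 139 of 140 responding, p = 0.9929 and se = sqrt(0.9929 × 0.0071/140) = 0.0071. The Wald limits are 0.9929 ± 1.645 × 0.0071, or 98.1% to 100.5%. At n = 140 the upper limit passes 100% with probability 0.19 at a true rate of 97% and 0.41 at 98%.

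**No failures.** One arm of 140 has no failures with probability 0.97^140 = 0.014, 0.98^140 = 0.059, 0.985^140 = 0.12 and 0.99^140 = 0.245. If both arms are at 100%, Wald gives [0, 0]. The Wilson lower limit is then 140/(140 + 1.645²) = 0.981, so Newcombe gives ±1.9 points.

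**The case against.** A reader might infer that Week 28 response will be near 100% and that the planned interval will collapse. The documents do not support that. They state no rate, response can be lost over 16 weeks, and SAP 17.2.2 Step 2 counts discontinuation and loss to follow-up as failures. Because the per-protocol set requires only one post-randomisation assessment, many such patients may remain in it. SAP 6.5 also allows exclusion for non-compliance or insufficient data, so the net effect is unknown.

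Over 85-95% the interval for the difference is close to nominal. At 99% in both arms Wald (0.909) is nearer to 0.90 than Newcombe (0.972). One arm without failures does not give a zero-width difference; that needs both arms at 100% in every imputed data set, and a single patient set to non-response in Step 2 prevents it.

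The poorest coverage belongs to per-arm limits. SAP 17.2.3.1 promises only counts and proportions by arm, with an interval for the difference. The Wald limits from Step 3 are not carried forward. Step 4 does produce per-arm limits at alpha 0.10, but no text says that they will be reported.

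All of this stands, and it limits the point to a minor one. It does not remove the built-in ceiling or supply a method for extreme proportions.

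**Conclusion.** The point holds as a minor improvement. Wald is the only interval planned for an endpoint that the entry rule pushes towards its upper bound. For the difference, the loss of coverage is about 0-3 points at equal rates of 85-98%, and reaches 5 points or more only when the rates are very high and unequal. For the per-arm limits of Step 4 it is about 2 points at 95%, 5 at 97%, 11 at 98% and 13 at 99%, and limits can pass 100%. A zero-width interval for the difference is possible but unlikely unless both rates reach about 98.5%.

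These figures rest on assumed response rates, roughly 130-165 patients per arm, and no between-imputation variance. They concern PASI 50; no case is made here that the higher PASI thresholds or sPGA are affected. The endpoints are secondary, with no margin, test or success rule.

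**What to change.** In SAP 17.2.2 and 17.2.3, specify before unblinding a Wilson score interval for each arm and a Newcombe 90% interval for the difference, pooled with a multiple-imputation version of the Wilson interval. Apply this to PASI 50 at least. A lighter alternative is to keep Wald and name the score intervals as a fallback for extreme proportions, with the trigger fixed in advance. State also whether the per-arm limits from Step 4 will be reported.

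The protocol names Wald too, so the departure should be recorded in SAP 3.3, which currently lists no changes.

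The cost is a few lines of SAP text and modest programming. The intervals become slightly wider and sometimes conservative near 100%. Little is lost if rates prove lower: Newcombe coverage is 0.904 at 90% response and 0.913 at 95%.
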